Undergoing an operation is a major stress for both children and their families, with up to 50% of the children reported to have significant perioperative anxiety (1). High levels of perioperative anxiety in children manifest as tension, irritability and increased autonomic nervous system activity (2,3); and are associated with a multitude of adverse clinical outcomes, including increased postoperative analgesia requirement, increased postoperative emergence delirium, increased postoperative behavioural changes (e.g. nightmares, postoperative separation and general anxiety, eating problems that can persist up to 2 weeks after surgery). (1) Furthermore, it impacts patient and parental satisfaction, creating an overall negative experience for families and staff.

The multifaceted risk factors of perioperative anxiety in children warrant a multi-modal array of tools up anaesthesiologists' sleeves to tailor for different children's needs based on age, understanding of instructions, and temperament (3). While pharmacological anxiolytics, e.g. Dexmedetomidine and Midazolam, are commonly deployed and effective, it has its limitations, such as time to effect, patient's age, as well as paradoxical agitation reported up to 10% for Midazolam, as well as taking away a learning opportunity for children to cope with stress. (4) Common non-pharmacological approaches include parental presence during induction of anaesthesia, distraction techniques, and educational approaches.

Traditional educational approaches often involve providing information to children and parents/legal guardians by written pamphlets, either physical or video tour of the operating room, recovery area, and orientation of medical equipment. With the advance of technology, children are often familiar and easily engaged with technological devices, including smart phones, tablets, video games, and even immersive virtual reality (VR). VR is increasingly utilized in clinical setting, providing a fun and engaging educational experience for children.

VR utilizes a head-mounted display with visual, auditory and tactile stimuli to simulate a fully immersive 3-dimensional environment. Its application in the paediatric perioperative setting can be either as distraction during painful procedures or during induction of anaesthesia, or as an exposure

tool in preoperative education. A meta-analysis of the effect of VR on preoperative anxiety shows a significant reduction of preoperative anxiety in paediatric patients (5). Ryu et al. utilized a famous cartoon character in the VR preoperative educational video and showed significant reduction in preoperative anxiety when compared to children receiving information through conventional means. (6,7) This benefit of VR exposure in reducing preoperative anxiety is not only evident in numerous studies (8-10) measuring anxiety score, but also demonstrated in studies measuring salivary cortisol concentration. (11, 12)

In a joint project involving the Department of Computing of Hong Kong Polytechnic University, the Department of Computer science Center for Innovative Applications of Internet and Multimedia Technologies of the City University of Hong Kong and the Hong Kong Children's Hospital (HKCH), an immersive VR operating theatre tour will be designed as part of preoperative education for children. A simulation of the perioperative journey in HKCH operating theatre will be created to help children form realistic expectations of their perioperative journey, and virtual exposure of different medical equipment helps children cope with their worries for the anticipated procedures. Parents/legal guardians will be able to monitor the VR experience on tablets via the monitoring software, which displays what the children see in VR. Given the fact that the capacity of conventional approaches, e.g. child-play involvement by child-life specialists are hugely limited now due to COVID pandemic, such a VR-enabled approach may help to alleviate patient's anxiety.

Aims and objectives

This study hopes to demonstrate the clinical effectiveness of virtual reality exposure in reducing children's perioperative anxiety in Hong Kong Children's Hospital.

Design and setting

This is a prospective and randomized controlled trial.

Children who are planned to undergo elective surgeries in Hong Kong Children's Hospital will be recruited in the study upon pre-anaesthetic assessment at clinic where written parental informed consent and paediatric assent (for patients ≥ 7 years old) will be obtained. For patients aged 5-6, assent would be carried out by the study team through verbal communication. Everyone will receive standard medical care and provided with information regarding the perioperative journey as per usual practice, including watching an introductory video in the waiting room area with accompanying adults, receiving perioperative education by a pre-anaesthetic nurse, as well as having an opportunity to have any questions answered by an anaesthesiologist in the pre-anaesthetic assessment clinic.

On the day of surgery where they are admitted for pre-surgery preparation, participants will complete a baseline anxiety assessment using the modified Yale Perioperative Anxiety Scale (mYPAS) (T0) (14) by a blinded researcher, after which they will be randomly assigned to intervention group (VR group) and conventional group (Non-VR group). Children assigned to the VR group will watch the designed VR immersive experience with headset, whereas children assigned to the non-VR group will receive standard medical care without any additional intervention. (Figure 1)

[figure not shown]

Figure 1. The overall hardware setup and connections.

All children will receive local anaesthetic cream to their dorsum of hands (EMLA or Ametop for those with contraindications to EMLA). Parents/legal guardians will accompany their children into the operating theatre until children are induced and unconscious unless parental refusal to do so. Patients will be allowed to lie down on the operating table, or sit up if preferred, when monitors including SpO₂ probe, Blood pressure cuff, and 3-lead ECG are applied. Anaesthesiologists, who are blinded by the allocation, will conduct induction using either intravenous induction or inhalation induction. Inhalation induction would be used for those who refuse intravenous cannula placement or those who have received >1 failed attempt of intravenous cannula placement. Another set of mYPAS (T1), Induction compliance checklist and Procedure behaviour rating scale will be performed by a blinded researcher (either research assistant or anaesthesiologist involved) on the patient when they are on the operating table right before induction of anaesthesia. Parents/legal guardians will be asked to fill in the State-Trait Anxiety Inventory (STAI) after accompanying their child during induction and while waiting outside.

As primary outcome is measured at the start of induction and anaesthesiologists are blinded from the allocation, the conduct of anaesthesia, including drugs of choice for induction and maintenance, analgesia, and airway intervention, will be performed as per usual practice which is not standardized. Intravenous induction will comprise of an opioid (either Remifentanil 0.1-0.2mcg/kg/min or 1-2mcg/kg Fentanyl), Propofol (either 2-4mg/kg bolus or TCI Paedfusor starting with Cp 5mcg/mL titrated until patient is unconscious) with 1mL of 0.5% Lignocaine to alleviate sting caused by propofol, +/- muscle relaxant of choice as required. Inhalational induction will comprise of using a mask smeared with artificial flavouring of choice, administering O₂/N₂O/ Sevoflurane mixture. After securing airway with either laryngeal mask or endotracheal tube, patients will be maintained on total intravenous anaesthesia with Propofol under Paedfusor Cp model or Sevoflurane/O₂/Air. Patients will be given adequate multi-modal analgesia and anti-emetic as per usual practice, and will be extubated in operating theatre after the surgery. Parents/legal guardians will accompany the patients again in the recovery room as soon as possible. Lastly, parents/legal guardians will provide feedback by completing a parental satisfactory score.

[figure not shown]

Figure 2: Flowchart of assessments and interventions for recruited patients

Hypothesis

We hypothesize that virtual reality preparation can significantly reduce anxiety in children, defined as 20% reduction in mYPAS score at induction compared to control group.

Inclusion and exclusion criteria

Inclusion criteria:

- Age 5-12years old
- American Society of Anaesthesiologist (ASA) physical status I or II
- Undergo elective surgical procedures which requires general anaesthesia
- No previous experience of anaesthesia or surgery

Exclusion criteria:

- Patients who are undergoing ultra-major surgery requiring postoperative intensive care unit care.
- Patients who are blind, or with hearing impairment
- Patients with significant developmental or cognitive delays, ADHD or autism
- Patients with history or current symptoms of vertigo
- Patients with history of epilepsy or seizures
- Patients who require anxiolytic premedication
- Patients who have physical conditions that prohibit use of headsets e.g. head / facial injuries, open skin or infectious condition on head/face, head/ facial malformation that precludes proper fitting of the VR headset
- Non-Cantonese speaking patients (due to limited resources of having Cantonese speaking VR design)
- Patients and/or parents/legal guardians who refuse to participate in study

Sample size and statistical analysis

A previous study (17) measuring perioperative anxiety in children at induction reported a mean mYPAS of 30.1 with a SD of 8.4. Using this data, a sample size of 30.1 for each arm is at least required to detect a 20% reduction in mYPAS score to achieve an alpha of 0.5 and power of 80%. We aim to recruit 96 children-parent pairs in order to account for 37.5% dropout rate due to change of surgery or anaesthesia plan, or loss to follow-up, as well as to increase the power for studying secondary outcomes.

Mann-Whitney U test will be applied to compare non-parametric data such as mYPAS score, induction compliance checklist, procedural behaviour rating scale and parental satisfactory score. Statistical significance will be accepted for $p < 0.05$. Baseline categorical variables will be analyzed using the X² test or the Fisher exact test.

Outcome and measurements

Primary outcome is whether there is a significant reduction of anxiety of children at induction, defined by a 20% reduction in the modified Yale Preoperative Anxiety Scale (mYPAS) between control group and intervention group at T1.

mYPAS is considered the gold standard in assessing preoperative anxiety in children (14), consisting of 27 items divided into five domains: activity, emotional expressivity, state of arousal, vocalization and use of parents/legal guardians, ranging from 23.3 to 100. A cut-off of $>/= 30$ indicates a high anxiety level in children.

This instrument has been considered as a gold standard instrument for measuring preoperative anxiety and had been administered in many previous studies. mYPAS will be assessed by a blinded researcher or anaesthesiologist, at induction in the operating theatre.

Secondary outcomes include baseline preoperative anxiety score using mYPAS at T0 (conducted before randomization by a blinded researcher), Induction compliance checklist, procedural behaviour rating scale, parental anxiety is evaluated by State-trait anxiety inventory (STAI), and parental satisfactory score.

Randomization and Blinding

Block randomization with stratification of age groups (5-8 years old, 9-12 years old) will be performed in a 1:1 allocation ratio.

The study will be single-blinded where the assessors and anaesthesiologists conducting the anaesthesia will be blinded by the following arrangement: The preoperative baseline mYPAS will be conducted before allocation, and the assessor at induction will not be involved in the allocation process. Anaesthesiologists and recovery nurses are blinded and encouraged not to actively discuss the use of VR with patients and parents/legal guardians.

Data handling and record keeping

To protect patient privacy, all research data would be handled in line with HA/Hospital's policy in handling/storage/destruction of patients' medical records. They would be locked in cabinets where the department keep confidential information. Electronic data should be saved in secured computer of the hospital with restricted access. Data collected will be destroyed after 3 years of publication.

Ethical Implication

All patients will receive standard medical care including information regarding the perioperative journey. VR itself is a non-invasive intervention, and patients will be reassured that they can terminate the VR appliance any time if they experience any discomfort. Although concerns of the risk of false memory formation have been raised, as children of young age may not be able to differentiate actual experience and imaginary play, adverse events are rarely reported. Risks of physical injury through collision into nearby objects while using the VR headset can be minimized by monitoring children in a spacious empty room devoid of obstacles.

Besides, the issue of confidentiality is the major ethical issue, and will be solved by recording the data in a manner that does not allow the participants to be identified (i.e. using a non-recognizable code for each participants).

This study will be conducted in compliance with Declaration of Helsinki and ICH-GCP.

Study significance

VR is an innovative technology with extensive applications in procedural anxiety and pain alleviation. Showing its effect on perioperative anxiety in children in our locality will give us a sustainable, simple, and non-pharmacological option of improving children's coping and the perioperative journey for children and parents/legal guardians.

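### The sample-size paragraph prints alpha as 0.5 against its own p < 0.05 rule and gives a fractional 30.1 per arm; at the stated dropout, 96 recruits leave 30 per arm

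*Combined protocol and SAP*

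**What the plan says.** All the figures are in the combined protocol and SAP, under Sample size and statistical analysis.

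- **Planning values:** an earlier study that "reported a mean mYPAS of 30.1 with a SD of 8.4".
- **Requirement:** "a sample size of 30.1 for each arm is at least required". The stated target is a "20% reduction in mYPAS score to achieve an alpha of 0.5 and power of 80" per cent.
- **Recruitment:** "We aim to recruit 96 children-parent pairs". Two reasons are given. The first is an allowance for losses: "in order to account for 37.5% dropout rate due to change of surgery or anaesthesia plan, or loss to follow-up". The second concerns the other endpoints: "as well as to increase the power for studying secondary outcomes".
- **Analysis:** "Mann-Whitney U test will be applied to compare non-parametric data such as mYPAS score". The threshold follows: "Statistical significance will be accepted for" p < 0.05.

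Two other places matter. The Hypothesis section defines the target as a 20% lower mYPAS score at induction than in the control group, which is a directional statement. Randomization and Blinding sets 1:1 allocation. The plan does not say whether the test is one-sided or two-sided.

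**The concern.** Four things in one short paragraph do not fit together.

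1. The planning alpha (0.5) is ten times the testing alpha (0.05).
2. The required size is a fraction of a child, although it is described as a minimum and should therefore have been rounded up.
3. The recruitment target, reduced by the plan's own dropout rate, does not quite reach that minimum.
4. The target is also justified by added power for secondary outcomes, yet the dropout allowance appears to use up the whole margin.

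This paragraph is the plan's only justification for enrolling 96 children. Ethics reviewers and later readers depend on alpha, required size and expected completers, and as printed they cannot reproduce the requirement.

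**Working it through.** **Inputs from the plan.** Control mean 30.1, SD 8.4, 20% reduction, power 80%, 1:1 allocation, 96 recruited, 37.5% dropout. Sidedness is not given, so both options are shown.

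Difference to detect: 0.20 x 30.1 = 6.02 points. Standardised difference: d = 6.02 / 8.4 = 0.7167.

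**Step 1. Reproduce the stated size.** Normal formula per arm: n = 2 (z_alpha + z_beta)^2 / d^2, with z_beta = 0.842. The t-test column solves the same problem with the noncentral t distribution.

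| Alpha | Normal formula | t-test |
|---|---|---|
| 0.5, two-sided | 8.95, so 9 | 8.42, so 9 |
| 0.05, one-sided | 24.07, so 25 | 24.78, so 25 |
| 0.05, two-sided | 30.56, so 31 | 31.55, so 32 |

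For the two-sided 0.05 row: 2 x (1.960 + 0.842)^2 / 0.7167^2 = 30.56. Of these settings, only two-sided 0.05 comes near the stated 30.1, and the printed alpha of 0.5 does not.

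**Step 2. Could rounded inputs explain 30.1?** Means from 30.05 to 30.149 combined with SDs from 8.35 to 8.449 give 30.10 to 31.02 by the normal formula at two-sided 0.05. The stated value lies at the lower edge of that range, and every value in the range rounds up to at least 31.

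**Step 3. Completers at the stated dropout.** 96 x (1 - 0.375) = 60, or 30 per arm. Working back from the printed minimum: 2 x 30.1 / 0.625 = 96.32, slightly more than 96. Working back from 30 per arm: 60 / 0.625 = 96 exactly. At 37.5% dropout nothing is left over beyond 30 per arm.

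**Step 4. Power.** Normal formula: power = Phi(d x sqrt(n/2) - z_alpha). For n = 30 and two-sided 0.05: 0.7167 x sqrt(15) - 1.960 = 0.816, so power is 79.3%.

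| Per arm | Normal, two-sided 0.05 | t-test, two-sided 0.05 |
|---|---|---|
| 30 | 79.3% | 77.9% |
| 31 | 80.6% | 79.3% |
| 32 | 81.8% | 80.6% |
| 48 (no dropout) | 94.0% | 93.5% |

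The shortfall from 80% at 30 per arm is 0.7 points (normal) or 2.1 points (t-test). Under one-sided 0.05, power at 30 per arm is 87.1% or 86.4%, and there is no shortfall.

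**Step 5. Dropout at which 80% is still reached (two-sided).** Normal formula, 62 completers: 1 - 62/96 = 35.4%. t-test, 64 completers: 1 - 64/96 = 33.3%.

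**The case against.** **The alpha is an obvious missing zero.** The next paragraph gives the correct threshold, and correcting the figure changes no patient, test or decision. This stands, and it limits the severity. A reader might infer that the trial accepts a 50% false-positive rate or was sized on that basis. The documents do not support this: the rule for declaring significance is p < 0.05, and alpha 0.5 would have led to about 9 per arm.

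**The shortfall against the printed minimum is a tenth of a child.** The figure 30.1 is also the mean mYPAS quoted in the sentence before it, so it may be a copying slip, and 60 / 0.625 = 96 suggests planning with 30 per arm. If so, the mismatch between 30.0 and 30.1 disappears. Rounding the expected VR mean from 24.08 to 24 (an assumption) would make the difference 6.1 and the normal formula 30.56 x (6.02/6.1)^2 = 29.77, so 30. None of this can be settled from the documents, and the sponsor should therefore be asked for its calculation. The printed figure still needs replacing.

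**The secondary-outcome sentence can be read charitably.** It may mean that 96 tolerates dropout up to 37.5% and yields extra power if fewer are lost. That reading is fair; the plan should say so.

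**Keeping 96 leaves target and requirement slightly apart.** Full consistency at 37.5% dropout would need 100 recruits (62/0.625 = 99.2) or 104 (64/0.625 = 102.4), with equal arms. Given a gap of at most 2.1 points, stating what 96 delivers is enough.

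**Two stronger inferences fail.** A reader might conclude that the trial is materially underpowered. The gap is small, exists only if the test is two-sided, and closes at somewhat lower dropout. A reader might also conclude that the planned Mann-Whitney test has less power than the two-means figures. That would rest on a normal shift model, which does not fit here. The expected VR mean, 24.08, is only 0.78 above the scale minimum of 23.3, and with SD 8.4 a normal model would put about 46% of VR scores below that minimum. The documents do not give the shape of the scores near the floor, so neither the direction nor the size of the difference can be stated.

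**Conclusion.** The paragraph is wrong as written; severity is minor to moderate.

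- **Certain from the documents alone:** alpha 0.5 contradicts the testing rule and does not reproduce the stated size. The minimum of 30.1 is not a usable number of children. At 37.5% dropout, 96 recruits give 30 per arm, with no surplus beyond that.
- **Conditional on two-sided 0.05:** the required size is 31 (normal formula) or 32 (t-test) per arm, and power at the assumed dropout is about 78-79% against the stated 80%.
- **If one-sided 0.05 was intended:** 25 per arm suffice and there is no power gap, but alpha and the printed size still need correcting.

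The misprinted alpha does not cause the shortfall in completers; the two are separate. No effect size is given for any secondary outcome, so power for those is not assessed.

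**What to change.** 1. Correct alpha to 0.05.
2. Have the sponsor confirm whether it is two-sided and which calculation was used.
3. Replace 30.1 with one whole number and name its method: if two-sided, 31 by the normal formula or 32 by the t-test, but not both.
4. Keep 96 and state what it delivers.

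Possible wording if two-sided and the t-test are confirmed:

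> Using a two-means t-test calculation as an approximation (control mean 30.1, SD 8.4, 20% reduction, two-sided alpha 0.05, 80% power), 32 children per arm are required. We will recruit 96 pairs. At 37.5% dropout, 30 per arm would complete and approximate power would be 78%; 80% is reached with 64 completers (dropout up to 33.3%). Power for secondary outcomes is increased only if dropout is below 37.5%.

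For the normal formula, the corresponding figures are 31 per arm, 79%, 62 completers and 35.4%. If one-sided is confirmed, the size and power figures must be restated on that basis. Apart from calling the calculation a two-means approximation, the text should claim nothing about the power of the Mann-Whitney test.

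Cost: one paragraph and one query to the sponsor. No added patients and no change to design or analysis.

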Appendix:

Modified Yale Perioperative Anxiety Scale (14)

Calculation of score: Highest score of the observed behaviour is the score of each category. A partial weighted score is calculated by dividing the score by the total items of that category. All categories used are added together, multiply by 100 and divided by the number of categories used.

Activity

 1. Looking around, curious, playing with toys, reading (or other age-appropriate behavior); moves around holding area/treatment room to get toys or to go to parent; may move toward operating room equipment 2. Not exploring or playing, may look down, fidget with hands, or suck thumb (blanket); may sit close to parent while waiting, or play has a definite manic quality 3. Moving from toy to parent in unfocused manner, non-activity-derived movements; frenetic/frenzied movement or play; squirming, moving on table; may push mask away or cling to parent 4. Actively trying to get away, pushes with feet and arms, may move whole body; in waiting room, running around unfocused, not looking at toys, will not separate from parent, desperate clinging
Vocalizations

 1. Reading (nonvocalizing appropriate to activity), asking questions, making comments, babbling, laughing, readily answers questions but may be generally quiet; child too young to talk in social situations or too engrossed in play to respond 2. Responding to adults but whispers, "baby talk," only head nodding 3. Quiet, no sounds or responses to adults 4. Whimpering, moaning, groaning, silently crying 5. Crying or may be screaming "no" 6. Crying, screaming loudly, sustained (audible through mask)
Emotional expressivity

 1. Manifestly happy, smiling, or concentrating on play 2. Neutral, no visible expression on face 3. Worried (sad) to frightened, sad, worried, or tearful eyes 4. Distressed, crying, extreme upset, may have wide eyes
State of apparent arousal

 1. Alert, looks around occasionally, notices or watches what anesthesiologist does (could be relaxed) 2. Withdrawn, sitting still and quiet, may be sucking on thumb or have face turned into adult 3. Vigilant, looking quickly all around, may startle to sounds, eyes wide, body tense 4. Panicked whimpering, may be crying or pushing others away, turns away
Use of parents

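### The comparison of T1 mYPAS leaves the pre-randomisation T0 score unused and lists T0 as a secondary outcome: valid, but probably less precise than it could be

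*Combined protocol and SAP*

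**What the plan says.** Under Design and setting, on the day of surgery "participants will complete a baseline anxiety assessment using the modified Yale Perioperative Anxiety Scale (mYPAS) (T0) (14) by a blinded researcher", and assignment follows. The second score, T1, is taken "on the patient when they are on the operating table right before induction of anaesthesia". Outcome and measurements makes the between-arm comparison at T1 the primary outcome.

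Sample size and statistical analysis says "Mann-Whitney U test will be applied to compare non-parametric data such as mYPAS score, induction compliance checklist". No adjusted model, change score or other use of T0 in the T1 comparison appears anywhere in the document. T0 is placed elsewhere: "Secondary outcomes include baseline preoperative anxiety score using mYPAS at T0 (conducted before randomization by a blinded researcher".

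Randomization and Blinding says "Block randomization with stratification of age groups (5-8 years old, 9-12 years old) will be performed in a 1:1 allocation ratio", but the analysis text does not mention the strata.

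The planning values come from a study that "reported a mean mYPAS of 30.1 with a SD of 8.4", with a target reduction of 20%. The scale is described as "ranging from 23.3 to 100".

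**The concern.** A score taken before allocation on the same instrument as the primary outcome is often its best predictor. If T0 predicts T1, adjusting for it removes between-child variation from the comparison, using data the trial already plans to collect. An unadjusted test gives that up. There is little slack: 96 recruited less 37.5% dropout leaves 60 children, or 30 per arm.

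Listing T0 as an outcome is a separate, smaller fault. VR cannot change a score taken before allocation, so a between-arm test of T0 could only test the randomisation. The plan does not expressly call for that test, but its general reference to the mYPAS score would cover it.

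**Working it through.** **Reproducing the plan's own figure.** The target difference is 0.20 × 30.1 = 6.02 and the SD is 8.4. With two-sided alpha 0.05 and 80% power, n per arm = 2 × [8.4 × (1.960 + 0.842) / 6.02]² = 30.56. The plan prints 30.1. The printed alpha of 0.5 would give 9 per arm, so 0.05 is used below. The recruitment target follows: 60 / (1 − 0.375) = 96.

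**What T0 could buy in the simplest case.** With T0-T1 correlation ρ, adjustment multiplies the variance by 1 − ρ². The documents give no ρ, so a range is assumed. By normal approximation, power at 30 per arm is 79.3% (ρ = 0), 82.9% (0.3), 89.3% (0.5) and 93.4% (0.6).

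**The floor.** That approximation ignores the shape of the scale. The Appendix says "A partial weighted score is calculated by dividing the score by the total items of that category"; the category values are then averaged and multiplied by 100. With four categories of 4 levels and one of 6:

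- Minimum: (4 × 1/4 + 1/6) × 100/5 = 23.33.
- Smallest step: 100 / (6 × 5) = 3.33, so the next possible score is 26.67.
- Planned VR mean: 30.1 × 0.8 = 24.08.
- Largest share of VR children above the minimum: (24.08 − 23.33) / 3.33 = 22.4%. At least 77.6% must sit exactly at it.

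This holds if all five categories are scored and the planned mean occurs. Ties on that scale favour a rank method.

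**Simulation.** Tests were two-sided at 0.05, with 6000-8000 trials per power cell (4000 for model 3 at the planned effect) and Monte Carlo SE about 0.5 points. Mann-Whitney was tie-corrected. Rank ANCOVA regressed midranks of T1 on arm, ranked T0 and age stratum. The score models were:

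1. Normal, control mean 30.1, SD 8.4, shift 6.02.
2. As 1, with values below 23.3 set to 23.3. The observed difference becomes 4.04, with 21% of control and 46% of VR at the floor.
3. 23.3 plus a gamma variable, control mean 30.1, SD 8.4, VR mean 26.
4. Five categories driven by one latent normal (loading 0.8), combined by the Appendix rule, control mean 30.1, SD 8.4, VR mean 26. At the floor are 45% of control and 72% of VR. Latent correlations of 0.3, 0.5 and 0.6 give observed ones of 0.21, 0.37 and 0.44.

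Power (%) at 30 per arm:

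| Model | Mann-Whitney | Rank ANCOVA, ρ = 0 | 0.3 | 0.5 | 0.6 |
|---|---|---|---|---|---|
| 1 | 75-76 | 75 | 77 | 85 | 90 |
| 2 | 71-73 | 71 | 76 | 82 | 86 |
| 3 | 62-63 | 63 | 65 | 73 | 79 |
| 4 | 62-63 | 63 | 65 | 67 | 70 |

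Power (%) at 48 per arm (96 / 2, no dropout):

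| Model | Mann-Whitney | Rank ANCOVA, ρ = 0.3 | 0.5 | 0.6 |
|---|---|---|---|---|
| 1 | 92-93 | 94 | 97 | 99 |
| 2 | 90-91 | 92 | 95 | 97 |
| 3 | 83 | 86 | 91 | 94 |
| 4 | 82 | 83 | 86 | 88 |

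At the planned VR mean of 24.08, Mann-Whitney already reaches at least 99.8% in model 3 and 98.4% in model 4, so there is no meaningful gain.

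**Checks on the alternative.** Rejection under the null was 4.6-5.6% for rank ANCOVA and 4.4-5.3% for Mann-Whitney. Rank ANCOVA was never more than 0.8 points below Mann-Whitney. ANCOVA on means with HC3 errors can lose to Mann-Whitney at 30 per arm: at zero correlation, 67% against 72% (model 2) and 58% against 63% (model 4). The age stratum added about 1 point or less in a normal model with age explaining 2-10% of variance.

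**The case against.** The strongest reply is that nothing here is wrong: the test is valid, and at the planned effect the models that respect the floor and the planned means show no gain. In models 3 and 4 the gain appears at a VR mean of 26, a reduction of (30.1 − 26) / 30.1 = 13.6%, which is an assumption of this review. **This stands.** It limits the benefit to a smaller true effect or more spread-out scores than planned.

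The largest gains come from the least realistic models. Model 1 allows impossible scores below 23.3. In model 2 the planning values are latent; after censoring, the control mean is about 31.1, the SD 6.9 and the VR mean 27.1. **This also stands**, so model 4, the only one using the Appendix scoring, deserves most weight: gains of about 2 to 8 points at latent correlations of 0.3 to 0.6.

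The correlation may be low. T0 and T1 fall on the same day but in different settings, T1 may be scored by a research assistant or the anaesthesiologist, and children needing anxiolytic premedication are excluded. **This is fair**, and is why the range includes zero.

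The bound on ties assumes five scored categories; without the parent category the minimum is (3 × 1/4 + 1/6) × 100/4 = 22.9. Rank ANCOVA also gives no effect in points, and preferring it to other adjusted methods is partly judgement. In one coarser floored gamma run (VR excess over the floor halved, zero correlation, 30 per arm), ordinary ANCOVA on means reached 50% power against 40% for both rank methods.

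These points limit the size of the gain and the choice of method. They do not show that leaving T0 out is better, or that it belongs among the outcomes.

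**Conclusion.** The point holds as a cheap improvement, with medium confidence. The plan is valid, but its only named test for T1 mYPAS ignores T0 and the age strata, and T0 is misclassified as an outcome. The misclassification needs no assumption.

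The precision gain rests on an assumed T0-T1 correlation and score shape. At correlations of 0.3 to 0.6, 30 per arm and the effects simulated, it runs from about 2 points of power to about 15. The low end is the better guide if scores follow the Appendix grid. The gain is nil at zero correlation, and negligible at the planned VR mean in models 3 and 4. The cost in power was under one point, so the exchange favours adjustment.

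**What to change.** Before any outcome data are seen by arm, amend Sample size and statistical analysis and Outcome and measurements:

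- **Primary analysis:** rank ANCOVA, with midranks of T1 mYPAS regressed on arm, ranked T0 mYPAS and age stratum (5-8, 9-12), two-sided 0.05.
- **Sensitivity analysis:** the unadjusted Mann-Whitney test.
- **Supporting estimate:** the T0- and stratum-adjusted mean difference in points with a robust 95% CI, not used as the primary test. Its coverage in simulation was 95-96% in models 2 and 4, but 93-94% in model 3 at 30 per arm.
- **T0 mYPAS:** move it from the secondary outcomes to the baseline covariates, with no between-arm test.
- **Missing T0:** state how it is filled in without using arm, so that no child with a T1 score is lost.

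The cost is wording and a slightly more complex analysis, with no new data or visits.
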